7.2 Randomization and Blinding

Eligible subjects will be randomized in a 4:3 ratio to receive TRC101 or placebo, stratified by their baseline blood bicarbonate value (≤ 18 versus > 18 mEq/L) and screening eGFR value (< 30 versus ≥ 30 mL/min/1.73m 2):

- 6 g TRC101 administered QD for 12 weeks (n≈120)
- placebo administered QD for 12 weeks (n≈90)

At least half of the subjects enrolled in the study will have a baseline blood bicarbonate value of 12 to 18 mEq/L.

In this study, [REDACTED]

[REDACTED] each study site must have an unblinded Pharmacist or designated unblinded study staff member (the “Pharmacist”) for handling (dispensation and collection) of the study drug. These individuals will be responsible for dispensing study drug (including supervision of administration of the first dose of study drug) and collecting used and unused study drug containers and dosing diaries. If study drug dose needs to be adjusted or interrupted per the titration algorithm (see TRCA-301 protocol, [Appendix 2](#)), such adjustments will be performed in a blinded manner in both active and placebo treatment groups. The designated unblinded study staff member(s) will not have any other responsibilities for the study except for performing study drug dispensation and collection, assessing dosing compliance and performing drug accountability and entering related data in the electronic case report forms (eCRFs). The subjects, Investigators, Medical Monitors, Tricida, site personnel (including all those involved in collection of safety information) and CRO staff (except for those responsible for monitoring of unblinded data) will remain blinded to the subject’s treatment assignment throughout the study until after the database is locked and access to the randomized treatment codes has been authorized. The DMC members and the statisticians responsible for reporting to the DMC will be unblinded during the study.

The Pharmacist must not inform the subjects, Investigators, Medical Monitors, Tricida, or other site or CRO personnel about the subjects’ treatment assignment. In case of a medical emergency,

the Investigator may obtain the treatment assignment for the subject from the interactive response technology (IRT) system if such information is considered important to the management of a medical emergency. In such cases, the Investigator must submit a written report, including all pertinent details, to a Medical Monitor within 24 hours of the unblinding. The Investigator should make every reasonable attempt to contact a Medical Monitor before unblinding the subject. Additional details on study blinding are described in the Blinding Plan.

7.3 Assessments

Table 1 shows the schedule of events of the study.

7.3.1 Efficacy Measurements

Fasting blood bicarbonate levels measured onsite with an i-STAT point-of-care device will be used to determine the primary and secondary efficacy endpoints for this study. Exploratory efficacy measurements include: repeated chair stand test, and kidney disease quality of life questionnaire (KDQOL) Question 3. Other efficacy measurements include blood and urine biomarkers related to bone and kidney health.

7.3.2 Safety Measurements

Safety will be assessed by repeated clinical evaluation, including adverse events, serious adverse events (SAEs), vital signs, physical examination, 12-lead electrocardiograms (ECGs), and clinical laboratory tests (chemistry, hematology, coagulation, and urinalysis) from central laboratories.

7.3.3 Other Measurements

Spot urine will be used to evaluate urine electrolytes. 24-hour urine collections will be used to characterize albumin, sulfate, uric acid and urea nitrogen excretion.

8 SAMPLE SIZE AND POWER

8.1 Primary Efficacy Endpoint

The primary efficacy endpoint is having a change from baseline (CFB) in blood bicarbonate ≥ 4 mEq/L or having blood bicarbonate in the normal range (22 to 29 mEq/L) at the end of treatment (Week 12 Visit). This outcome is termed a “response”.

The sample size in this study is based on the efficacy results observed in the Phase 1/2 Study TRCA-101. The table below shows 46% of TRC101-treated subjects and 3% of placebo-treated subjects had an increase of ≥ 4 mEq/L or had blood bicarbonate in the normal range (22 to 29 mEq/L) after 2 weeks of treatment. We assume the full TRC101 treatment effect had not been reached during the short (2-week) treatment period.

Results from Study TRCA-101

Blood Bicarbonate (mEq/L)	Pooled TRC101 (n=104)	Pooled Placebo (n=31)
Number (%) of Subjects at Week 2 (Day 15)		
CFB ≥ 4	41 (39.4%)	1 (3.2%)
Normal (22 - 29)	37 (35.6%)	0
Composite (CFB ≥ 4 or Normal)	48 (46.2%)	1 (3.2%)
95% Exact CI of Composite	36.3%, 56.2%	<0.1%, 16.7%

CFB = Change from baseline; CI = confidence interval.

In Study TRCA-301, we expect that 50 to 55% of TRC101-treated and 10% of placebo-treated subjects will have an increase of ≥ 4 mEq/L or have blood bicarbonate in the normal range at the end of treatment (Week 12 Visit). A Fisher's exact test with a 0.05 two-sided significance level will have over 99% power to detect this difference if the study has 90 placebo and 120 TRC101 subjects. If the true proportion of TRC101 subjects who respond at the Week 12 Visit is indeed between 50% and 55% and if no more than 5% of subjects have missing data at Week 12, the study will have roughly 90% power to result in a 95% confidence limit with a lower bound of at least 35% and 40%, respectively.

8.2 Secondary Efficacy Endpoint

The secondary efficacy endpoint is change from baseline in blood bicarbonate at the end of treatment (Week 12 Visit).

In the Phase 1/2 Study TRCA-101 after 2 weeks of treatment, we observed the following with regard to the change from baseline in blood bicarbonate level:

Results from Study TRCA-101

	TRC101	Placebo
Mean CFB at Week 1 (Day 8)	2.3	0.83
Mean CFB at Week 2 (Day 15)	3.3	-0.18
Common SD	2.5	
Treatment × Time effect	P = 0.2248	
Baseline blood bicarbonate (Covariate)	P <0.0001	
Correlation between Week 1 and Week 2	0.667	0.333

CFB = change from baseline; SD = standard deviation

In Study TRCA-301, we expect to observe the following mean change from baseline in blood bicarbonate over time for each group, with between group variance of 1.871, between time point variance of 0.08, and time point × treatment variance of 0.23.

Treatment	Time Point						
	Week 1	Week 2	Week 4	Week 6	Week 8	Week 10	Week 12
Placebo	0.85	0.75	0.65	0.55	0.45	0.35	0.25
TRC101	2.00	2.50	3.00	3.50	3.75	4.00	4.25

We assume a constant standard deviation to be 3.0 mEq/L and correlation as shown in the table below:

	Week 1	Week 2	Week 4	Week 6	Week 8	Week 10	Week 12
Week 1	1	0.6	0.399	0.265	0.176	0.117	0.078
Week 2	0.6	1	0.6	0.399	0.265	0.176	0.117
Week 4	0.399	0.6	1	0.6	0.399	0.265	0.176
Week 6	0.265	0.399	0.6	1	0.6	0.399	0.265
Week 8	0.176	0.265	0.399	0.6	1	0.6	0.399
Week 10	0.117	0.176	0.265	0.399	0.6	1	0.6
Week 12	0.078	0.117	0.176	0.265	0.399	0.6	1

We calculated power and sample size for the mixed-effect repeated measures (MMRM) model based on (nQuery Advisor software) a univariate two-group repeated measures analysis of variance using the Greenhouse-Geisser correction to nominal degrees of freedom. This study will have 99% power to detect a variance among the group marginal means of 1.871 mEq/L, will have 85% power to detect a variance of 0.08 among the means of the 7 time points (i.e., Weeks 1, 2, 4, 6, 8, 10, and 12), and will have 99% power to detect an interaction between groups and time points with a variance of 0.23, assuming that the between groups error term is 5.32, the within groups

error term is 2.4, the measure of "sphericity" of the covariance matrix, epsilon, is 0.69, (its estimate, the Greenhouse-Geisser correction, has an expected bias of about $g_1/(2n-2)$ where g_1 is -2.38) when the significance level is 0.05 and the sample size in each of the two groups is 104 subjects (approximation to 90 placebo and 120 TRC101 subjects, respectively).

9 ANALYSIS SETS

9.1 Modified Intent-To-Treat

The modified intent-to-treat (MITT) analysis set is defined as all randomized subjects who had both baseline and at least one post-baseline blood bicarbonate value measured using the i-STAT device. The MITT analysis set will be used for evaluation of efficacy, based on planned treatment assignment.

9.2 Per-Protocol

The per-protocol (PP) analysis set is defined as MITT subjects, who completed the 12-week treatment period without important protocol deviations (See Section 12.2) and with $\geq 80\%$ study drug dosing compliance. The PP analysis set, which will be based on the planned treatment assignment, will be used for evaluation of efficacy.

9.3 Safety Analysis Set

The safety analysis set is defined as all subjects who received any amount of study drug (TRC101 or placebo). The safety analysis set, which will be based on the actual treatment received, will be used for evaluation of safety. Placebo-treated subjects who received any amount of TRC101 during the treatment period will be assigned to the TRC101 treatment group from the time when TRC101 was received.

10 GENERAL CONSIDERATIONS

The analysis sets as defined in Section 9 will be used for efficacy and safety analyses. Subject listings of all analysis data that support summary tables and/or figures will be provided along with their source data from the eCRFs. Measurements from subjects excluded from the pre-defined analysis sets or extra measurements (such as unscheduled or repeat assessments) will not be included in summary tables unless specified otherwise but will be included in the subject listings.

In general, subject listings will be sorted by treatment group, subject number, assessment date (time, and parameter, as applicable).

For most summary statistics, data will be analyzed and displayed by treatment group. Unless otherwise specified, descriptive statistics for continuous variables will include the number of subjects with data to be summarized (n), mean, standard deviation (SD), median, minimum and maximum. The same number of decimal places as in the observed value will be presented when reporting minimum and maximum; 1 more decimal place than in the observed value will be presented when reporting mean and median; and 2 more decimal places than in the observed value will be presented when reporting SD.

All categorical/qualitative data will be presented using frequency counts and percentages. All percentages will be presented to 1 decimal place, unless otherwise specified. Percentages equal to 100 will be presented as 100% and percentages will not be presented for zero frequencies. Where individual variable values are missing, categorical data will be summarized based on reduced denominators (i.e., only subjects with available data will be included in the denominators). For summaries of AEs and concomitant medications (CMs), the percentages will be based on the number of subjects who received study drug.

Results of statistical analyses will be reported using summary tables, listings, and figures (TLFs). The ICH numbering convention will be used for all TLFs. The following conventions will be followed:

- Unless otherwise noted, all statistical testing will be two-sided and will be performed at the 0.05 significance level.
- Tests will be declared statistically significant if the calculated p-value is <0.05, unless otherwise specified.

All analyses and summaries will be produced using SAS® version 9.4 or higher.

Note that while the SAP predominantly uses the term ‘blood bicarbonate’ the TLFs will use ‘serum bicarbonate’.

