Appendix 2: Study Drug Titration Algorithm

Blood Bicarbonate (mEq/L)	Before Week 4 Visit	Week 4 through Week 11
< 12*	Evaluate for new acute acidotic process, contact Medical Monitor. Maintain dose pending discussion with Medical Monitor	Evaluate for new acute acidotic process, contact Medical Monitor. Maintain dose pending discussion with Medical Monitor.
12 to < 22	Maintain dose until next scheduled visit.	Increase the study drug dose by 1 packet/day (maximum dose is 3 packets/day). Only increase the dose if NO dose changes have been made during the previous 14 days. Retest blood bicarbonate at next scheduled visit.
22 to < 27	Maintain dose until next scheduled visit.	
27 to 30	Decrease the study drug dose by 1 packet/day (minimum dose is 0 packets/day). Invite subject for a visit in approximately 1 week to retest blood bicarbonate. Only decrease the dose if NO dose changes have been made during the previous 14 days.	
> 30*	Interrupt (hold) study drug. Invite subject for a visit in approximately 1 week to retest blood bicarbonate. If blood bicarbonate at that visit is: 
• < 27 mEq/L, restart study drug at a lower dose (1 packet/day less than before dose interruption).• ≥ 27 mEq/L, continue to hold the dose and retest again in approximately 1 week.	

* Blood bicarbonate value of < 12 mEq/L or > 30 mEq/L must be confirmed by a repeated measurement from a separate blood draw.

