10.1.5 Multiple Records at a Time Point

For analysis purposes, the mean value of multiple measurements collected at the same position (i.e., supine, standing, etc.) on the same visit day will be summarized for the corresponding protocol defined time point. All collected measurements and the mean values will be listed.

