10.2 Analysis Windows

Clinical visits may occur outside protocol-specified windows. Therefore, instead of relying solely on visit labels in the clinical database, analysis visits and their windows are defined using Study Day (See Section 10.1.2). For the purposes of data analysis and summary, assessments and/or measurements will be flagged based on the collection date/time that is closest to the protocol-scheduled time point (or target Study Day). Analysis visit windows are presented in Table 2 by type of assessments and/or measurements.

Table 2 Analysis Visit Windows

Protocol Scheduled Time Point	Target Study Day	Analysis Visit Windows (Study Day)					
		All Other Assessments	Hematology Urinalysis Spot Urine Pregnancy Tests	Repeated Chair Stand KDQOL Biomarkers	24-Hour Urine Collection	ECG	Body Weight
Screening 1	-14	$\leq -8^*$	$\leq -8^*$	-	-	-	-
Screening 2	-1	-7 to -1*	-	-	-	-	-
Day 1	1	1*	-7 to 1*	-14 to 1*	-14 to 1*	-	$\leq 1^*$
Week 1	8	2 to 11	-	-	-	-	-
Week 2	15	12 to 22	-	-	-	2 to 28	-
Week 4	29	23 to 36	-	-	-	-	2 to 42
Week 6	43	37 to 50	2 to 63	-	-	29 to 63	-
Week 8	57	51 to 64	-	-	-	-	43 to 70
Week 10	71	65 to 78	-	-	-	-	-
Week 12	85	79 to 90	64 to 91	≥ 2	64 to 91	71 to 91	-
Week 13	92	91 to 97	-	-	-	-	-
Week 14	99	≥ 98	≥ 92	-	-	≥ 92	≥ 92

* Use visit designation for scheduled visits; otherwise use the visit window.

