15.1 Safety Variables

Safety variables include:

1. AEs, SAEs and withdrawal of study drug due to AE
2. Having met the high bicarbonate dose interruption criterion (confirmed > 30 mEq/L) at any time during the Treatment Period
3. Laboratory test results
4. Vital signs
5. Body weight
6. Findings from 12-lead ECG

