15.3 Incidence of High Bicarbonate

A summary table will be provided with number and percentage of subjects who had a bicarbonate > 30 mEq/L by time interval during the Treatment Period. The table will also include total number of subjects and total number of occurrences during the Treatment Period.

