16 CHANGES RELATIVE TO THE PROTOCOL-SPECIFIED ANALYSIS

16.1 Other Efficacy Analyses

SAP Section 14.8 contains additional efficacy and dosing analyses that were not described in the protocol as follows:

- Additional categorical thresholds of bicarbonate increase (≥ 2 mEq/L and ≥ 3 mEq/L) was added to further understand potential treatment effect on bicarbonate increase in lower ranges.
- Baseline descriptor of kidney failure risk at 2 and 5 years (i.e., Kidney Failure Risk Equation score) was added to describe baseline kidney failure risks in the study population.

- Analyses exploring the effects of starting dose and dose titration.

While the protocol specified one of the safety endpoints as “Having met the high bicarbonate dose interruption criterion (confirmed > 30 mEq/L) at any time during the Treatment Period.”, SAP Section 15.3 describes summaries of subjects who had a bicarbonate > 30 mEq/L event. Removing the “confirmed” qualifier should capture any subjects potentially meeting the high bicarbonate dose interruption criterion at any time during the Treatment Period.

17 Reference

1. Yuan Y. Sensitivity Analysis in Multiple Imputation for Missing Data, SAS Institute Inc. <http://support.sas.com/resources/papers/proceedings14/SAS270-2014.pdf>
2. Tangri, et al. A predictive model for progression of chronic kidney disease to kidney failure JAMA. 2011;305(15):1553-1559
3. Hays RD, et al. Kidney Disease Quality of Life Short Form (KDQOL-SFtm), Version 1.3: A Manual for Use and Scoring. Rand, 1997.

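### SAP 10 and 10.2 leave threshold exceedances seen only at unscheduled or retest visits out of the Table 4 counts, and SAP 15.3 does not say which bicarbonate readings it counts

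*SAP*

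**What the plan says.** **Which values enter summary tables.** SAP 10 sets a default for all summaries: "extra measurements (such as unscheduled or repeat assessments) will not be included in summary tables unless specified otherwise". Such values still go into the listings. SAP 10.2 assigns records to windows by study day, and "assessments and/or measurements will be flagged based on the collection date/time that is closest to the protocol-scheduled time point". SAP 10.1.5 adds that "the mean value of multiple measurements collected at the same position (i.e., supine, standing, etc.) on the same visit day will be summarized" for the matching time point.

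**How extremes are found.** Under Protocol Appendix 2 a bicarbonate below 12 or above 30 mEq/L "must be confirmed by a repeated measurement from a separate blood draw". For values of 27 to 30, and for values above 30, the instruction is: "Invite subject for a visit in approximately 1 week to retest blood bicarbonate". Protocol 7.11 places that one-week visit under unscheduled visits, with a window of ±1 day.

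**What is to be reported.** SAP 15.1 lists as a safety variable: "Having met the high bicarbonate dose interruption criterion (confirmed > 30 mEq/L) at any time during the Treatment Period". SAP 15.3 plans a table of the "number and percentage of subjects who had a bicarbonate > 30 mEq/L by time interval during the Treatment Period", with total subjects and total occurrences. SAP 16.1 explains that dropping the word confirmed "should capture any subjects potentially meeting the high bicarbonate dose interruption criterion at any time during the Treatment Period". SAP 15.4 counts subjects beyond the Table 4 limits at each time point. For bicarbonate these limits are < 10, < 12, > 30 and > 32 mEq/L; potassium, creatinine, eGFR and others are also listed.

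**The concern.** The protocol looks for high bicarbonate partly through repeat draws and extra visits, and the SAP's default removes just those readings from the tables. Protocol 3.2.2 names an exaggerated pharmacological effect as a possible risk, and the high-bicarbonate criterion is one of the protocol's two safety endpoints. A subject whose only value above 30 comes at a retest has already been singled out by a reading of 27 to 30, yet could be missing from the summary.

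The low end has a different weakness. Protocol 6.11.1 says that an isolated fall in bicarbonate is not an adverse event, even when clinically significant. If a value below 12 or 10 is seen only at an unscheduled visit, the adverse event tables will not pick it up either.

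**Working it through.** The documents give no expected rate of bicarbonate above 30, so there is no planned figure to reproduce. Two checks follow.

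**1. Can a one-week retest supply a window value?**

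Inputs: target days and the all-other-assessments windows from SAP Table 2, and a retest 7 ± 1 days after a scheduled visit held on its target day (Protocol Appendix 2 and 7.11). Distance = |retest day − target day of the window it falls in|.

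| Visit before retest (target day) | Retest days | Falls in window of | Days from that target |
|---|---|---|---|
| Week 1 (8) | 14, 15, 16 | Week 2 | 1, 0, 1 |
| Week 2 (15) | 21, 22, 23 | Week 2, 2, 4 | 6, 7, 6 |
| Week 4 (29) | 35, 36, 37 | Week 4, 4, 6 | 6, 7, 6 |
| Week 6 (43) | 49, 50, 51 | Week 6, 6, 8 | 6, 7, 6 |
| Week 8 (57) | 63, 64, 65 | Week 8, 8, 10 | 6, 7, 6 |
| Week 10 (71) | 77, 78, 79 | Week 10, 10, 12 | 6, 7, 6 |

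If the visit before the retest is itself a day early or late, the smallest distance falls to 5. For example, a Week 2 visit on Day 14 allows a retest on Day 20, and |20 − 15| = 5. A visit on Day 16 allows Day 24, and |24 − 29| = 5. A scheduled visit held within ±1 day is at most 1 day from target, so it always wins. Only the Week 1 retest coincides with a scheduled visit. For the other five, the value is barred by SAP 10 as unscheduled and, even if admitted, is not chosen under 10.2 when the scheduled visit is attended.

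**2. What happens to a repeat draw on the same day?**

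Let the first reading be a and the repeat b.

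- Confirmed event: a > 30 and b > 30, so (a + b)/2 > 30. If b is dropped instead, a > 30 remains. The event is counted either way.
- Unconfirmed reading: a > 30 and b ≤ 30. If b is dropped, a still counts. If the two are averaged, the event may vanish: a = 31 and b = 29 give (31 + 29)/2 = 30.0, which is not above 30.

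Averaging can therefore remove only unconfirmed readings. As an illustration, take a total SD of 3.0 mEq/L, borrowed from the change-from-baseline SD in SAP 8.2. The visit mean and the within-visit SD are assumptions. The chance of a first reading above 30 is 1 − Φ((30 − mean)/3.0). The other columns come from 4 million simulated pairs per row and within-visit SD.

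| Assumed mean | P(first > 30) | Share of first readings > 30 removed by averaging, within-visit SD 0.5 / 1.0 / 1.5 | Confirmed events removed |
|---|---|---|---|
| 21.75 | 0.3% | 17% / 38% / 59% | 0 |
| 24 | 2.3% | 13% / 28% / 45% | 0 |
| 26 | 9.1% | 9% / 20% / 33% | 0 |

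For scale, one subject is 1/120 = 0.8 percentage points in the TRC101 arm and 1/90 = 1.1 in the placebo arm.

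**The case against.** The best reply is that SAP 15.3 and 16.1 together already specify otherwise. They drop confirmation, refer to any time in the Treatment Period, use intervals where Table 4 uses time points, and ask for total occurrences. That is a fair reading of intent, and it is why one cannot say that the 15.3 table will undercount. But those sections change the definition of the event and are silent on which records are eligible. Two programmers could follow the SAP faithfully and report different counts. The reply also does nothing for Table 4, where no text can be read as an exception.

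Second, nothing disappears. All values are listed, exceedances of the Table 4 limits are flagged in the listings (SAP 15.4), and dose interruptions are tabulated by arm (SAP 13.3). This stands: it is a reporting gap, not a loss of data. The interruption table is only a proxy for a confirmed value above 30, because Protocol 6.11.4.3 also allows interruption as an action taken for an adverse event.

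Third, SAP 10.1.5 is worded around body position, so its use for repeat blood draws is doubtful. It also sits badly with SAP 10: a repeat that is excluded cannot be averaged. This too stands, and the averaging effect is therefore conditional.

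A reader might go further and infer that the confirmed endpoint itself is undercounted because repeats are dropped or averaged. Check 2 shows that this is wrong for events found at a scheduled visit. A reader might also infer that the loss falls mainly on the TRC101 arm. That is plausible, but the documents give no rates by arm to support it.

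**Conclusion.** The point holds for Table 4. As written, exceedances seen only at unscheduled or retest visits are left out of the laboratory threshold summaries. This covers bicarbonate > 30, > 32, < 12 or < 10, and potassium, creatinine or eGFR extremes. It rests on the text of SAP 10, 10.2 and 15.4 and, for the one-week retests, on the scheduled visit having been attended.

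For SAP 15.3 the finding is an ambiguity. The table can miss subjects who first exceed 30 at a retest, and further occurrences in the same subject. If 10.1.5 is applied to blood draws, it can also miss unconfirmed first readings, against the aim stated in 16.1. Separately, 15.1 lists the confirmed criterion but no table for it is described.

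The size of any undercount cannot be derived from the documents. The 9% to 59% range concerns unconfirmed readings only, under assumed means and within-visit SDs, and is not an estimate for this trial. The change is worth making because the events are few and the safety count would otherwise depend on a programmer's reading.

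**What to change.** Add to SAP 15.3, and to 15.4 for the Table 4 laboratory thresholds only, a sentence such as: *All readings after the first dose and within the Treatment Period, whether scheduled, unscheduled or repeat, are counted individually and are not averaged; Sections 10 and 10.1.5 do not apply to these counts.*

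Then:

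- Add an any-time-on-treatment row that counts each subject once, by worst value.
- Report by arm both any value > 30 and confirmed > 30 mEq/L, so that the criterion in 15.1 has a table. State how the first and confirming readings are paired in the data.

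Do not extend the no-averaging rule to Tables 5 and 6. ECGs are taken in triplicate and the ECG baseline is a mean (SAP 10.1.14). Blood pressure and respiratory rate are taken in triplicate at Week 12 but once at other visits after baseline (Protocol 6.4). Counting single readings there would give some visits more chances to cross a limit and would compare single ECG readings with an averaged baseline.

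The cost is a few sentences and a little programming, with no new data. The reported incidence may come out slightly higher.
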